## **Study Summary**

To establish the feasibility of a future fully powered trial of early hearing aid provision in people with Mild Cognitive Impairment (MCI) and hearing loss in terms of delaying the onset of dementia. The pilot trial will test recruitment, attrition, and acceptability of two interventions: the hearing and healthy ageing interventions. During the COVID-19 pandemic, the trial will instead pilot a remotely delivered version of the active intervention of early hearing aid provision and support to test recruitment, feasibility, and acceptability (the Remote Hearing Intervention or RHI sub-study).

#### 1 Introduction

#### 1.1 Purpose and scope of the statistical analysis plan

This document describes the main statistical analyses to be applied to the data from the TACT Trial.

## 1.3 Analysis organisation

Unmasking of the data and the final analysis will be performed after the last patient has completed follow-up, all relevant data have been entered, checked, and locked, the analysis plan has been finalised and approved.

## 1.4 Data checking

Before analysis, basic checks will be performed to check the quality of the data. Incomplete or inconsistent data include:

- Missing data
- Data outside expected range
- Other inconsistencies between variables e.g. in the dates the questionnaires were completed

If any inconsistencies are found, the corresponding values will be double checked with the researchers and corrected if necessary. All changes will be documented by the trial statistician.

## 2 Description of the trial

TACT is a pilot randomised, parallel group trial in participants with MCI and hearing loss. Participants with hearing loss and MCI will be randomised to a hearing intervention (home-based provision of hearing aids, and adherence support) or a healthy ageing intervention (home-based educational intervention, to match intensity of social contact). Participants will be assessed on their hearing, cognition, quality of life, physical activity, mood, social interactions, and daily function at baseline and 6 months. During the COVID-19 pandemic the RHI sub study is conducted to pilot a remotely delivered version of the active intervention of early hearing aid provision and support and to test recruitment, feasibility, and acceptability. This single arm non-randomised sub-study will have a 4-week follow-up.

#### Main inclusion/exclusion criteria

Participants will be 55 years of age or older, with a diagnosis of MCI, and with mild to moderate adult-onset hearing loss, community-dwelling, without any self-reported hearing aid use in the past month.

For the single-arm RHI sub-study participants who had consented for the randomised trial prior to the onset of COVID-19 will be invited to participate.

## Sample size

With 76 randomised participants, we will achieve the following 95% confidence intervals (CI) for our expected estimates of dropout, acceptability of the intervention, and difference in hearing aid adherence between the Hearing Intervention and Healthy Ageing Intervention at the end of trial:

- 1. Estimate attrition rate of 20% randomised participants with complete follow-up at 6 months, 95%CI [10% to 30%].
- 2. Acceptability of the Hearing Intervention: proportion of participants allocated to the Hearing Intervention completing ≥2 intervention sessions expected value ≥80% of intervention group, 95% CI with n=76 would be [70% to 90%].
- 3. Difference in daily hearing aid adherence between arms: target of 50% difference between the Hearing Intervention and Healthy Ageing Intervention arms in the proportions of participants maintaining hearing aid use at 6 months (end of follow-up), 95% CI with n=76 would be [ 31% to 69%] with 20% attrition it would be [29.5% to 71%].

A minimum of 10 and up to 12 participants will be recruited to the RHI sub-study.

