#### 3 Data collection

#### 3.1 Primary outcome measures

This pilot trial aims at establishing the feasibility of a full-size trial of the hearing aid intervention versus healthy ageing intervention in people with MCI. This future trial will be a scaled-up version of the present pilot, modified with any lessons learnt in the current trial. The pilot's primary objective is therefore to establish feasibility of recruitment, randomisation, retention, and the acceptability of the trial interventions as follows:

- Recruitment: Proportion of eligible participants who are randomised into the trial.
- Attrition: proportion of participants who are lost to follow-up at 6 months of trial duration, and endpoint measures are not obtained.
- Acceptability of the Hearing Intervention: proportion of participants allocated to the Hearing Intervention completing >2 intervention sessions.

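### The confidence interval stated for acceptability uses the total of both arms (76), although only the Hearing Intervention arm is in the denominator, so the stated precision is not achieved

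*SAP*

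**What the plan says.** SAP section 2 describes a two-arm design: "TACT is a pilot randomised, parallel group trial in participants with MCI and hearing loss", with participants randomised to a hearing or a healthy ageing intervention. The Sample size section opens with the trial total: "With 76 randomised participants, we will achieve the following 95% confidence intervals (CI". It then lists three expected estimates, each with an interval.

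Item 2 concerns acceptability. Its quantity is the "proportion of participants allocated to the Hearing Intervention completing ≥2 intervention sessions". The expected value and the precision follow in the same line: "completing ≥2 intervention sessions expected value ≥80% of intervention group, 95% CI with n=76 would be [70% to 90" per cent.

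Section 3.1 lists the same quantity among the primary outcomes, again with a one-arm denominator: "Acceptability of the Hearing Intervention: proportion of participants allocated to the Hearing Intervention completing >2 intervention sessions". The session threshold is written differently in the two places. That is a separate matter and does not change the arithmetic at an assumed 80%.

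**The concern.** A proportion defined on one of two randomised arms cannot have every randomised participant in its denominator. If the interval was computed with 76, or with any number close to it, it is narrower than the trial can deliver.

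This matters because of how 76 is justified. Section 6.2 says that no sample size calculation based on significance tests was done and that P-values will not be reported. In this SAP, interval width is therefore the only argument for the sample size, and acceptability is one of three primary outcomes. Someone planning the full trial would take item 2 to mean that an observed 80% excludes acceptability below 70%.

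**Working it through.** **Inputs**
- Total randomised, both arms: 76 (SAP, Sample size).
- Denominator: the Hearing Intervention arm only (Sample size item 2; section 3.1).
- Expected proportion p = 0.80, the floor of the stated range (item 2).
- Confidence level 95%, z = 1.96.
- Allocation ratio: not stated in the SAP. 1:1 is assumed, and other ratios are shown.

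**Step 1: reproduce the stated figure.** The Wald half-width is z × √(p(1−p)/n).
- n = 76: 1.96 × √(0.16/76) = 0.090, giving 71.0% to 89.0%.
- n = 76 with continuity correction, adding 1/(2 × 76) = 0.0066: half-width 0.0965, giving 70.3% to 89.7%. This rounds to the stated 70% to 90%.
- n = 61, which is 76 × 0.8 = 60.8 rounded (76 less 20% attrition over both arms): 1.96 × √(0.16/61) = 0.100, giving 70.0% to 90.0%.

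Either route to the stated interval counts participants from both arms. Item 1 points the same way. Its attrition interval of 10% to 30% around 20% concerns all randomised participants and has the same half-width. Since 0.2 × 0.8 = 0.8 × 0.2, equal half-widths imply the same n.

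**Step 2: can 76 mean the Hearing Intervention arm alone?** The opening sentence says not, and item 3 agrees. Item 3 gives a between-arm difference of 50 points as "95% CI with n=76 would be [ 31% to 69%] with 20% attrition it would be [29.5% to 71" per cent, so its half-width before attrition is 19 points. With 76 in each arm, the half-width for a 50-point difference is at most 1.96 × √(2 × 0.75 × 0.25/76) = 13.8 points (75% v 25%). So 76 is the two-arm total.

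**Step 3: recompute with the arm that contributes.**

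| Allocation (assumed) | n in Hearing Intervention arm | Wald half-width, points | Wald 95% CI |
|---|---|---|---|
| 1:1 | 38 | 1.96 × √(0.16/38) → 12.7 | 67.3% to 92.7% |
| 2:1 | 51 | 1.96 × √(0.16/51) → 11.0 | 69.0% to 91.0% |
| 3:1 | 57 | 1.96 × √(0.16/57) → 10.4 | 69.6% to 90.4% |

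Other methods at n = 38:
- Wilson at 80%: 64.8% to 89.7%.
- Clopper-Pearson: 62.7% to 90.4% at 30/38 and 65.7% to 92.3% at 31/38. Exactly 80% would be 30.4 participants, so both neighbouring counts are shown.

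**Step 4: n needed for ±10 points.** n = 1.96² × 0.16/0.10² = 61.5, so 62 in the Hearing Intervention arm alone. That is 62/76 = 82% of everyone randomised, or roughly 4:1 allocation.

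**The case against.** The best case on the other side has four parts.

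- **The ratio is unknown.** The SAP states none, and the protocol, which would normally hold it, was not available for this check. At 2:1 the interval is 69.0% to 91.0%, one point from the stated limits. This stands: the correction has to be conditional on the ratio, and 38 must not be written in as a fact. It does not remove the mismatch, because no ratio short of about 4:1 gives ±10 points.
- **The expected value is at least 80%.** At 85% with 38 in the arm, the half-width is 1.96 × √(0.85 × 0.15/38) = 11.4 points, giving 73.6% to 96.4%, so the lower limit exceeds 70%. That is true, but the stated interval is centred on 80% and has to be judged there.
- **Little depends on the figure.** The main outcomes are analysed descriptively, and this SAP sets no decision threshold at 70%. The outcome definition in section 3.1 already gives the final analysis the right denominator. This stands and limits the severity.
- **Item 3 may seem to settle the ratio or to contain its own error.** A reader might infer that its interval of 31% to 69% arises only with 38 per arm. It does not. With assumed proportions of 65% v 15%, 38 per arm gives 31.1% to 68.9%, and a 51/25 split gives 30.8% to 69.2%; both round to the stated limits. A reader might also infer that item 3's with-attrition interval is wrong because it is not symmetric about 50%. With 30.4 per arm, 60% v 10% gives 29.6% to 70.4% and 65% v 15% gives 28.8% to 71.2%. The discrepancy is at rounding level and depends on arm proportions that the SAP does not state, so no error is shown there.

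**Conclusion.** Item 2 is wrong as written: it attaches an interval based on both arms to a proportion defined on one. At 80% the Wald interval is about 67% to 93% under 1:1 (Wilson about 65% to 90%) and about 69% to 91% under 2:1, against the stated 70% to 90%. The half-width is therefore about 11 to 13 points instead of 10. Under 1:1, an observed 80% would not exclude a true acceptability of about two thirds.

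The mismatch itself rests on no assumption. Its size rests on the allocation ratio, an observed proportion of 80% and the choice of interval method.

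This should be fixed. A reader might infer that the sample size itself fails, or that the trial's conclusions are at risk. The document does not support that: this is a descriptive pilot, the SAP ties no decision to the 70% limit, and no analysis or participant is affected.

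**What to change.** Keep the total of 76. In Sample size item 2, replace the total with the number allocated to the Hearing Intervention under the trial's actual allocation ratio, state that ratio, and give the matching interval and its method. If allocation is 1:1, that is 38 in the arm and about 67% to 93% (Wald), or about 65% to 90% (Wilson). If it is 2:1, it is 51 and about 69% to 91% (Wald). Item 3's intervals need no change on this account.

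The cost is a change of SAP wording and a less favourable precision statement for one primary outcome. No extra participants and no change to the analysis are needed.

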#### 3 Data collection

#### 3.1 Primary outcome measures

This pilot trial aims at establishing the feasibility of a full-size trial of the hearing aid intervention versus healthy ageing intervention in people with MCI. This future trial will be a scaled-up version of the present pilot, modified with any lessons learnt in the current trial. The pilot's primary objective is therefore to establish feasibility of recruitment, randomisation, retention, and the acceptability of the trial interventions as follows:

- Recruitment: Proportion of eligible participants who are randomised into the trial.
- Attrition: proportion of participants who are lost to follow-up at 6 months of trial duration, and endpoint measures are not obtained.
- Acceptability of the Hearing Intervention: proportion of participants allocated to the Hearing Intervention completing >2 intervention sessions.

## 3.2 Secondary outcome measures

- Cognition (ACE), Trail Making Test (TMT), Delayed Word Recall Test (DWRT)
- Quality of Life (SF36,EQ-5D)
- Functioning (IADL Lawton-Brody Instrumental Activities of Daily Living), Social activities (SF-DEM), Loneliness (UCLA)
- Frailty (grip strength)
- Physical activity (accelerometer)
- Mood (GDS)
- Self-reported hearing (HHIE-S)
- Hearing aid usage: measured in hours per day by self-report. For some intervention arm participants logged data on hearing aid usage are also available.

In addition to continuous measures of hearing aid use, a binary measure of adequate hearing

aid use will be defined as a minimum of 4 hours a day on average since last trial assessment (when at home and in usual health) as defined at 6 months (end of trial), based on the hearing aid with the highest average use (as each participant has two hearing aids). Other data on adherence to the use of hearing aids will also be recorded, including the number of hearing aids lost by participants in the intervention arm.

#### Assessing diagnostic accuracy of hearing screening tools:

Single question, Shoebox, HearCheck, HHIE-S will be compared to the gold standard - Audiologist-delivered PTA (best ear average of the 4 PTA frequency values from 500 Hz to 4000Hz) to assess their accuracy in diagnosing hearing problems. In addition, agreement between Shoebox and audiologist delivered PTA will be assessed for the following: auditory thresholds at 500 Hz, 1000 Hz, 2000 Hz, 4000 Hz and average of the 4 frequencies.

## Outcome assessment for the RHI sub-study

At the end of the RHI there will be an outcome collection contact (contact 5). Outcome collection will be done at 4 weeks (+/2 weeks) after receiving the hearing aids (expected duration 45-60 minutes total). These will include the same assessment tools administered at the RHI sub-study baseline assessment (a simplified version of the TACT assessment battery), namely:

- Mood: Geriatric depression scale (GDS) [28]
- Cognition: Addenbrooke Cognitive Examination (ACE-III); these will include only those items that can be obtained by remote assessment

# 4 Baseline characteristics of participants

List of variables to be used to assess baseline comparability of the randomised groups:

- Age
- Sex
- Cognition scale: Addenbrooke Cognitive Examination (ACE-III) score, Trail Making Test (TMT) (Parts A & B), Delayed Word Recall Test (DWRT)
- Quality of life: SF36, EQ-5D
- Function: 4-item Lawton-Brody IADL
- Social activities: SF-DEM
- Loneliness: UCLA loneliness
- Frailty: grip strength
- Physical activity: as measured by accelerometery at baseline
- Geriatric Depression Score
- Self-reported hearing disability Hearing Handicap Inventory for the Elderly Screening version (HHIE-S)
- Hearing Threshold PTA average (best ear average of the 4 PTA frequency values from 500 Hz to 4000Hz)
- Quicksin: units in dB SNR loss (List 1 SNR Loss and List 2 SNR loss, to take as an overall average SNR loss per participant)
- Ethnicity
- Cardio-vascular history as assessed by:
  - o Diabetes
  - o High Blood Pressure
  - o Ischaemic Heart Disease
  - o Stroke
  - Smoking history

- Alcohol consumption/week
- History of falls
- Presence of Communication partner

# 5 Pre-intervention procedures for RHI sub-study (during COVID-19)

After consent, participants' baseline outcome measures will be obtained through remote interview. These will include

- Mood: Geriatric depression scale (GDS)
- Cognition: Addenbrooke Cognitive Examination (ACE-III); these will include only those items that can be obtained by remote assessment

## 6 Data analysis

## 6.1 Recruitment and representativeness of recruited patients

A CONSORT flow chart will be constructed. This will include the number of patients approached and assessed for eligibility, number of patients agreeing to enter the trial, then by treatment arm: the number continuing through the trial, the number withdrawing at each time point, the number lost to follow-up at each time-point and the numbers excluded/analysed.

## 6.2 Statistical Analysis

Summary measures for the baseline characteristics of the intervention and control groups will be presented as means and standard deviations or medians and inter-quartile ranges for continuous variables as appropriate, and frequencies and percentages for categorical variables. The number of missing observations will be reported.

Given this is a feasibility study, our main outcomes of interest are rate of recruitment, acceptability of randomisation, level of attrition and these data analyses will be descriptive using counts and proportions. The proportion adhering to the use of hearing aids, based on a predefined threshold of usage defined above, will be calculated for each trial arm and the difference in the proportions with 95% confidence intervals will be estimated. A logistic regression model will also be used to estimate the odds of adherence in the intervention group compared to the control group with 95% confidence intervals.

As part of the secondary analyses, linear regression will be used to estimate the intervention effect on hearing aid usage measured in hours. Additionally, we will investigate the relationship between the following individual-level potential predictors of adherence to hearing aids:

- Higher objective HL (average PTA at baseline)
- More awareness of HL issues (higher HHIE-S score at baseline)
- More cognitive impairment (lower total ACE-III score at baseline)
- More depressed (higher GDS score at baseline)

We shall perform descriptive analyses of adherence using hearing aid usage measured as both continuous and binary variables, as per categories below:

- Mild vs Moderate-Severe: mild defined as PTA average in better ear < 35dB
- HHIE-S: no handicap (defined as HHIE-S at baseline <9) vs handicap

- More cognitive impairment (defined as ACE-III total <83%)

- Above cut-off for depressed (GDS at baseline >=5) vs not depressed.

If appropriate (depending on sample size) we will also perform linear and logistic regression analyses to investigate association between these factors and hearing aid usage and present estimates of association with 95% confidence intervals.

Appropriate regression models adjusted for baseline values of the outcome will be used to estimate the intervention effect for some of the clinical and quality of life outcomes listed in section 3.2. Mixed effects models will be used to estimate the intervention effects for repeated measures outcomes adjusted for time and baseline values of the outcomes. The results from all regression analyses will be reported as estimates with 95% confidence intervals. Since this is a feasibility trial with no sample size calculation performed based on statistical significance tests, P-values will not be reported. Audiological measurements will be summarised descriptively. The agreement between self-reported hearing usage data and logged hearing data for the intervention arm will be compared using plots. The means for the self-reported and the logged hearing usage data will be calculated and compared descriptively. Diagnostic accuracy of hearing screening tools in comparison to the gold standard will be assessed by calculating sensitivity and specificity with corresponding 95% confidence intervals, as part of an exploratory analyses. Agreement between raters measuring hearing loss will be assessed using Kappa or spearman rank correlation as appropriate.

The quantitative data from the single arm RHI sub-study will be analysed using means/SD or medians/IQ range and counts/percentages as appropriate.

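### Section 6.2 sets no unequal-variance provision for the linear regression of hearing-aid hours, although only one arm is supplied with aids; its 95% CI can be off when completers differ appreciably between arms.

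*SAP*

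**What the plan says.** The hours analysis is secondary, and the plan is that "linear regression will be used to estimate the intervention effect on hearing aid usage measured in hours" (SAP section 6.2). The outcome is "measured in hours per day by self-report" (section 3.2). Section 6.2 adds that "The results from all regression analyses will be reported as estimates with 95% confidence intervals", and that P-values will not be reported.

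Three design features bear on the spread of hours in each arm:

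- The Hearing Intervention is "home-based provision of hearing aids, and adherence support" (section 2).
- The Healthy Ageing Intervention is a "home-based educational intervention, to match intensity of social contact" (section 2), with no supply of aids described.
- Entrants must be "without any self-reported hearing aid use in the past month" (Main inclusion/exclusion criteria).

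Section 6.2 names no type of standard error, covariate or assumption check for this model. Section 7 fixes Stata 16, whose default for linear regression assumes one residual variance.

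**The concern.** Control participants start with no recent use and are not given aids by the trial, so most should report zero hours. Hearing arm participants will range from non-use to many hours a day. A large difference in variance can therefore be foreseen before any data are seen.

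A pooled-variance standard error is harmless when the arms have equal numbers. When they do not, it leans towards the variance of the larger arm. If fewer Hearing participants complete, the interval is too narrow; if fewer controls complete, it is too wide. Attrition is one of the quantities that the pilot sets out to learn, so completer numbers by arm cannot be taken as equal in advance. With no P-value, the interval carries the stated uncertainty for the hours effect.

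**Working it through.** **Inputs from the SAP.** 76 randomised and 20% attrition (Sample size), so 0.8 × 76 = 60.8, about 61 completers. The SAP gives no mean, SD or interval for hours, no allocation ratio and no attrition by arm. Assumed here: 1:1 allocation (38 per arm) and the hours distributions below.

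**The nearest stated figure.** The Sample size section gives [31%, 69%] for a 50-point difference in adherence at n = 76. The Wald interval is 0.50 ± 1.96 × √[(p1(1−p1) + p2(1−p2))/38].

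- 65% v 15%: √(0.355/38) = 0.0967, giving [31.1%, 68.9%]. This reproduces the stated interval.
- 70% v 20%: √(0.370/38) = 0.0987, giving [30.7%, 69.3%]. This also reproduces it.
- 50% v 0%: √(0.250/38) = 0.0811, giving [34.1%, 65.9%]. This does not match. With a continuity correction it becomes [31.5%, 68.5%], which is close.

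For the interval with attrition, [29.5%, 71%], 60% v 10% at 30 per arm gives [29.4%, 70.6%]. Under plain Wald, then, the planning figures fit roughly 10% to 20% adequate use in controls, and about 0% only with a continuity correction. Control use of 0%, 10% and 20% is carried through below.

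**Standard errors.** Pooled: √[sp²(1/n1 + 1/n2)], with sp² = [(n1−1)s1² + (n2−1)s2²]/(n1+n2−2). Unequal-variance: √(s1²/n1 + s2²/n2). Take s1 = 4 h (Hearing) and s2 = 0 or 1.5 h (control), both assumed.

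- 27 Hearing / 34 control, s2 = 0: sp² = 26 × 16/59 = 7.05; pooled SE 0.684, correct SE 4/√27 = 0.770, ratio 0.89.
- 27/34, s2 = 1.5: sp² = (416 + 74.25)/59 = 8.31; 0.743 against 0.812, ratio 0.92.
- 34/27, s2 = 0: sp² = 33 × 16/59 = 8.95; 0.771 against 4/√34 = 0.686, ratio 1.12.
- 34/27, s2 = 1.5: sp² = (528 + 58.5)/59 = 9.94; 0.813 against 0.744, ratio 1.09.
- Equal arms: ratio 1.00 whatever the variances.

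**Coverage of the nominal 95% interval** (40,000 simulated trials per case, default regression). Set A: 85% users in the Hearing arm, gamma mean 6.5 h and SD 3.5 h; control users gamma mean 4 h and SD 2.5 h. Set B: a 50-point gap in the share of users (50/0, 60/10, 70/20), with users' hours gamma mean 8 h and SD 3 h in both arms. Hours are capped at 16.

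| Completers, Hearing/control | Set A: 0%, 10%, 20% control users | Set B: 0%, 10%, 20% |
|---|---|---|
| 29/32 | about 93–94% | 92.8%, 94.3%, 94.5% |
| 27/34 | 91.1%, 92.1%, 93.0% | 91.1%, 93.1%, 94.0% |
| 34/27 | 96.7%, 96.5%, 96.3% | 96.5%, 96.0%, 95.4% |

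HC3 stayed at 94.5% to 95.4% in set A, and Welch at 94.3% to 95.2% in set B.

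**How often such gaps arise.** With Binomial(38, 0.8) completers in each arm, the gap is 5 or more in 19.5% of trials and 7 or more in 6.1%, half of these (3.1%) in the too-narrow direction. A gap of 13 or more occurs in 0.03%. If dropout were 30% in one arm and 10% in the other (illustrative), a gap of 7 or more would occur in 63% of trials.

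**The case against.** The strongest reply is that little is lost on average. Averaged over random 20% dropout in each arm, with the set A hours, default coverage is 94.2%, 94.6% and 94.7% at 0%, 10% and 20% control users, against 94.7%, 95.0% and 95.0% for Welch. That is a cost of at most about half a point. The SAP also does not forbid robust standard errors: it says only linear regression. Hours are secondary, no decision rule rests on the interval, and section 6.2 also reports adherence as a difference in proportions and an odds ratio.

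All of this stands and limits the weight of the point. It does not remove it. The average hides a poorer interval in the trials where the gap is large, differential dropout between two unlike interventions cannot be excluded, and the default software interval is what the plan yields if run as written.

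A reader might infer more than the documents support:

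- **That the interval is wrong whenever completers differ.** Small gaps cost little, as the 29/32 row shows.
- **That control hours are known to be nearly all zero.** This is inferred from the design. The SAP does not say controls cannot obtain aids elsewhere, and its own planning interval fits some control use.
- **That leaving out baseline pure-tone average (PTA) is an error.** An unadjusted randomised comparison is valid. PTA ("Higher objective HL (average PTA at baseline") is listed for a separate analysis of predictors of adherence.

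**Conclusion.** The point holds as a minor one. Unequal arm variances are foreseeable from the design, and section 6.2 makes no provision for them. The effect on coverage is a shortfall of about 2 to 4 points (91% to 93%) at 27 Hearing against 34 control completers, and an excess of about 1 to 2 points at 34 against 27, under the set A hours with 0% to 20% control users. Set B gives a smaller effect once some controls use aids. Only the interval is affected, not the estimated difference in means. A sizeable loss needs an appreciable gap in completers together with low control use. Under equal 20% dropout, a gap of 7 or more arises in about 6% of trials. All these figures rest on assumed hours distributions and 1:1 allocation; the direction of the error follows from the variance formulas alone.

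**What to change.** In section 6.2, specify for the hours outcome either linear regression with heteroscedasticity-robust standard errors (HC3; in Stata, regress with vce(hc3)) or a Welch unequal-variance interval. Report the SD of hours and the share of zero-hour users by arm beside the estimate; both would also help to plan the full-size trial described in section 3.1.

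Adding baseline better-ear PTA as a covariate is optional. It might reduce the standard error by about 1% to 5% if it correlates 0.3 to 0.5 with hours in the Hearing arm, which is an assumption.

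The cost is one phrase and one software option, with no new data. With equal arms the HC3 standard error exceeds the pooled one by a factor √[n/(n−1)]; at 30 completers per arm this is √(30/29) = 1.017, so the interval is about 1.7% wider.

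### Agreement of Shoebox with audiologist thresholds in dB is planned, but the only statistics named are kappa and Spearman, and neither measures agreement on the dB scale

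*SAP*

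**What the plan says.** SAP section 3.2, under the subheading on diagnostic accuracy of hearing screening tools, sets two aims. The first is diagnostic accuracy of four tools, Shoebox among them, against a reference standard described as "Audiologist-delivered PTA (best ear average of the 4 PTA frequency values from 500 Hz to 4000Hz". The second is added to the first and is separate from it: "agreement between Shoebox and audiologist delivered PTA will be assessed for the following: auditory thresholds at 500 Hz". It continues with the other three frequencies and the four-frequency average.

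Section 6.2 gives the methods. For the first aim: "Diagnostic accuracy of hearing screening tools in comparison to the gold standard will be assessed by calculating sensitivity and specificity", with 95% confidence intervals, as exploratory work. For agreement on hearing loss there is one sentence: "Agreement between raters measuring hearing loss will be assessed using Kappa or spearman rank correlation as appropriate". That sentence does not name Shoebox.

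Section 6.2 also shows that the PTA average is a numeric quantity in dB whose absolute level is used in this trial: "mild defined as PTA average in better ear < 35dB". The section names no paired difference, limits of agreement, intraclass correlation or concordance coefficient for Shoebox against PTA.

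**The concern.** The aim concerns numeric thresholds, and the method sentence offers two statistics. Kappa applies only once the thresholds have been cut into categories, which discards the dB scale. Spearman applies to numbers but uses only their ranks. It shows whether the two methods put participants in the same order, not whether they give the same reading. A device with a constant offset, or one that stretches the scale, can have a very high Spearman coefficient.

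At stake is whether the pilot can report what section 3.2 sets out to learn. A coefficient of 0.90 reported under the heading of agreement invites the conclusion that the readings match, and it would be the same whether the device is unbiased or 15 dB out.

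**Working it through.** The SAP gives no sample size, target or expected value for this analysis, so there is no figure of its own to reproduce. The check is of the statistic's properties.

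**Step 1: exact property, no assumptions.** Let x be the audiologist threshold. Adding a constant (x + 10 dB) or multiplying by a positive constant (1.3x) leaves the ranks unchanged, so Spearman's rho is exactly 1.0 in both cases. Computation on simulated values confirmed 1.0 and 1.0.

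**Step 2: illustration with measurement error.** Inputs:
- From the SAP: 76 randomised participants (sample size section), used only to size the simulation, and the 35 dB line that section 6.2 uses to define mild loss.
- Assumed: PTA SD 9 dB; Shoebox error SD 4 dB; offset b of 0, 5, 10 or 15 dB; PTA mean 38 dB (needed only for kappa and classification).

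Formulas, with Shoebox = PTA + error + b:
- Pearson correlation r = 9/√(9² + 4²) = 9/√97 = 0.914. Under normality Spearman = (6/π)·arcsin(r/2) = 0.906. The offset b does not enter.
- Lin's concordance = 2·9²/(9² + 97 + b²) = 162/(178 + b²).
- Bland-Altman limits = b ± 1.96 × 4 = b ± 7.84.

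The Spearman and kappa columns come from 2,000 simulated trials of 76 pairs; the other columns come from the formulas.

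| Offset (dB) | Spearman | Lin's concordance | 95% limits of agreement (dB) | Kappa at 35 dB |
|---|---|---|---|---|
| 0 | 0.90 | 162/178 = 0.91 | −7.8 to 7.8 | 0.73 |
| 5 | 0.90 | 162/203 = 0.80 | −2.8 to 12.8 | 0.58 |
| 10 | 0.90 | 162/278 = 0.58 | 2.2 to 17.8 | 0.30 |
| 15 | 0.90 | 162/403 = 0.40 | 7.2 to 22.8 | 0.11 |

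**Step 3: sensitivity to the assumed SDs.** Spearman takes a single value for each pair of SDs, whatever the offset.

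| PTA SD / error SD (dB) | Spearman, any offset | Lin's, 0 dB | Lin's, +10 dB |
|---|---|---|---|
| 7 / 4 | 0.86 | 0.86 | 0.46 |
| 9 / 4 | 0.91 | 0.91 | 0.58 |
| 12 / 4 | 0.94 | 0.95 | 0.71 |
| 9 / 2 | 0.97 | 0.98 | 0.61 |
| 9 / 6 | 0.82 | 0.82 | 0.54 |

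The size of the fall varies, but in every row Spearman fails to register the offset.

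**Step 4: what the planned accuracy analysis would show.** With SD 9, error SD 4 and a +10 dB offset, from the bivariate normal distribution:

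| PTA mean / cut-off (dB) | Sensitivity, 0 → +10 dB | Specificity, 0 → +10 dB | Misclassified, 0 → +10 dB |
|---|---|---|---|
| 35 / 35 | 0.87 → 1.00 | 0.87 → 0.31 | 13% → 35% |
| 38 / 35 | 0.89 → 1.00 | 0.84 → 0.25 | 13% → 28% |
| 35 / 25 | 0.94 → 1.00 | 0.79 → 0.16 | 8% → 11% |
| 38 / 25 | 0.96 → 1.00 | 0.77 → 0.13 | 5% → 6% |

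The offset appears as lost specificity, but specificity is estimated only in people below the cut-off. With mean 35 and cut-off 35 that is half of 76, or 38 people. With mean 38 and cut-off 25 it is Φ(−13/9) = 7.4% of 76, or about 6 people.

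**The case against.** The strongest reply is that an offset would not pass unseen. Shoebox is among the tools whose sensitivity and specificity are planned, and step 4 shows specificity dropping from 0.87 to 0.31 at a 35 dB cut-off. Kappa, which is also named, drops from 0.73 to 0.30 at the same offset. Audiological measurements are also to be summarised descriptively, which could show different means. This part stands: a reader might infer that a biased device would simply be declared in good agreement, and the SAP does not support that. What remains is that these analyses work through classification. The sections concerned state no cut-off for the accuracy analysis (the 35 dB line belongs to the adherence subgroups), and few participants may lie below a lower one. None of them gives the size of the difference in dB at each frequency.

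A second reply is that the agreement sentence speaks of raters, leaves the choice open, and never assigns Spearman to Shoebox thresholds. That is fair as to wording: the link is an inference. But section 3.2 holds the only stated aim on agreement of hearing-loss measurements. If the sentence does not cover it, that aim has no named method, and the same fix is needed.

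Two further readings are tempting and fail. One is that Shoebox is meant to replace audiologist PTA, so that future participants would be misclassified. The SAP states no such plan, and the misclassification at +10 dB ranges from about 6% to 35% depending on the assumed mean and cut-off. The other is that the comparison of self-reported with logged hearing aid use has the same flaw. It does not: the SAP plans that "The agreement between self-reported hearing usage data and logged hearing data for the intervention arm will be compared using plots", and it adds that "The means for the self-reported and the logged hearing usage data will be calculated and compared descriptively". A comparison of means does detect an offset. That the two means would come from different people can only be inferred from the SAP's silence.

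**Conclusion.** The point holds for the Shoebox and audiologist comparison only. The named statistics do not measure agreement on the dB scale, and agreement on dB thresholds is a stated aim. That Spearman ignores a constant offset or proportional bias is exact and rests on no assumption. The illustrative size, Spearman fixed at about 0.90 while Lin's concordance falls from 0.91 to 0.40 over 0 to 15 dB, rests on assumed SDs and offsets. The kappa and classification figures rest also on an assumed mean and cut-off. None of these is an estimate of how Shoebox performs.

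This should be fixed, but it does not threaten the trial. The screening-tool work is exploratory, and recruitment, attrition and acceptability do not depend on it.

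**What to change.** In section 6.2, replace the agreement sentence for this comparison. For each of the four frequencies and for the four-frequency average, report the paired mean difference (Shoebox minus audiologist) with 95% CI and the Bland-Altman 95% limits of agreement, with the plot. Optionally add an absolute-agreement intraclass correlation or Lin's concordance coefficient with 95% CI. Name Shoebox and audiologist PTA in the sentence, so that the method is tied to the aim in section 3.2. Keep kappa for categorised results, with the cut-off stated, and keep Spearman at most as a supplement.

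The pilot is large enough for this to be informative. With 76 pairs and an error SD of 4 dB (both assumed for this analysis), the mean difference would be known to within 1.96 × 4/√76 = ±0.9 dB. The cost is a few lines of SAP wording, with the same data and the same software.
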